Physical Activity and Pacemaker Study NCT03052829 Initial Protocol approved: 12/21/2016 Phy

Overview of approach: Based upon our previous work, the overall experimental design of this study is a small pragmatic randomized controlled trial (RCT). A general study diagram of events and procedures is present in Figure 2. Potential subjects who fit inclusion/exclusion criteria will be approached for enrollment once they are identified as candidates for permanent pacemaker implantation or as patients with already implanted Medtronic Revo or EnRhythm pacemakers. Individuals with, on average, less than 2 hours/day of active minutes over the prior 3 months (based in the pacemaker's internal accelerometer daily active minute reading) will be eligible for randomization. For individuals enrolled at the time of pacemaker implantation, the average active minutes for the time period of 3-6 months following implantation will be used to assess eligibility for randomization. At the time of enrollment all subjects will have a detailed medical history obtained. Thirty participants will be randomized across 2 parallel groups: an intervention group (n=15), or a Patient Usual Care (PUC) group (n=15). The PAC intervention follows the 5 A's (Assess, Advise, Agree, Assist, Arrange) model, which has been shown to be an effective clinical counseling tool for other health behaviors.14 Implanted Medtronic Pacemaker accelerometer data will be used to Assess physical activity levels. Subjects in the low active group will be referred to an intervention expert on the study staff. Eligible patients will then be Advised of their activity levels, and migrate through the 5 A's intervention model for 12 weeks. A fuller description of the intervention is included below. At the end of the 12 week active intervention, subjects in the intervention arm will enter a maintenance phase for an additional 3 months. During the study, pacemakers will be interrogated remotely or at clinic visits every 3 months. All subjects in the intervention arm will be contacted every 2 weeks to assess how they are doing with respect to the intervention. The study schema is shown in Figure 1, described in accordance with the CONSORT statement's recommendations for randomized clinical trials. An outline of study procedures is presented in Table 1.

Study setting.

Subjects will be recruited from individuals who require permanent pacemaker placement at Froedtert Hospital and Zablocki VA Medical Center, both located in Milwaukee, WI.

Participant eligibility and recruitment.

Criteria for Enrollment and Randomization.

Inclusion Criteria:

1) Age \geq 55 years old

2) Clinical indication for placement of permanent pacemaker or currently implanted pacemaker

3) LVEF of \geq 50% by most recent echocardiogram.

4) Able to ambulate

5) Average active time of ≤ 2 hours/day based on Revo or EnRhythm Accelerometer read out for the 3 month period prior to enrollment

6) Able to take 650 steps over 10 minutes following pacemaker implantation (~2-2.5 mph walking speed)

Exclusion Criteria:

1) Follow up for implantation planned at a non-study center at the time of implantation.

2) Individuals with and expected life span of 1 year or less at the time of implantation

3) Known history of cognitive impairment or inability to follow study procedures

4) Lack of stable internet access

Randomization. Randomization will occur at the patient level. Upon potential eligibility being identified, subjects will be randomized in 3 blocks of 10 participants and randomized 1:1 to each study arm. We will enroll until we reach 15 subjects in each study arm who complete all study procedures. Randomization will be delivered via a random number generation sequence. Due to the nature of the trial, research staff, clinicians, and patients will not be blinded to patient assignment.

Physical Activity Counseling Intervention Group: The 12 week intervention is a multifaceted intervention that follows the 5 A's (Assess, Advise, Agree, Assist, Arrange) model, designed to be both simple to implement and follow for patients. It mimics a referral for education model that is used for patients who require a nutritionist or other specialist for behavioral modification. The intervention includes the following elements.

1) Assess: Subjects will undergo a physical activity assessment, utilizing the implanted Medtronic Pacemaker accelerometer data.

2) Advise: Eligible patients will be shown the graph from our recent publication demonstrating the relationship between decreased active minute time and mortality to help build the case that an intervention is necessary.

3) Agree: Those patients who agree enter into a shared decision making process to behavior change – in this case modifying physical activity behavior in an effort to decrease sedentary time.

4) Assist: The patient will receive a written prescription that includes their baseline Medtronic Pacemaker accelerometer data, and a target to increase their activity. Activity will be increased using the following:

a. Self-regulatory monitoring: A pedometer with a target to increase steps by 10% per week, to a target of 10,000 steps/day. A calendar will be given for patients to write down daily amounts.

b. Brief printed support materials – on different behavioral strategies to increase active behaviors

c. A list of freely available internet-resources

d. Bi-weekly telephone support: A member of the study staff will call each participant randomized to the PAC intervention group every other week. Calls will be limited to 5 minutes and used to offer support, advice, and solicit feedback.

5) Arrange: A follow-up visit will be arranged for week 12, to retrieve outcome data for physical activity from the implanted Medtronic Pacemaker accelerometer. Alternatively, data will be obtained through convenient methods.

Overall, our approach employs key strategies proven to increase the adoption and retention of lifestyle integrated habitual physical activity in older adults.15,16 These strategies included the use of frequent feedback,15 selfregulation of activity,17,18 education and practice in realistic behavioral change strategies and goal setting,16 and rewarding.19

Patient Usual Care (PAC) Group: The PAC group will undergo Implanted Medtronic Pacemaker Accelerometer data retrieval, but this data will not be shown to the patient, nor used to alter behavior. This group will follow their typical clinical routine, and therefore represent a usual care approach.

Communication of Physical Activity information: All individuals with pacemakers will undergo interrogation of their device every 3 months during entire study period, including intervention phase and follow-up phase.

Outcomes: The primary outcome for this study is the number of active minutes as measured by the Medtronics Implanted Pacemaker accelerometer.

Statistical Methods: Baseline demographic and clinical data will be compared between groups by unpaired t-tests, Chi-squared tests, or non-parametric equivalents as appropriate. The primary outcome will be compared between

Data Analyses

SPSS 24 and SigmaStat 12.5 were employed for data analyses. Data will be analyzed on a per protocol basis given that the goal of this pilot. Baseline characteristics will be compared between groups using unpaired t-tests, chi-

square, or Fisher's Exact test as. Differences in step counts and pedometer determine active time over the study period will be investigated using general linear models for repeated measures with the randomization group assignment as the between subjects variable and a three factor within subjects comparisons representing the three measurement time points with the Tukey test applied for post-hoc comparisons if significance of the overall models was detected. Correlations between step count measurements and PDAH measurements were performed using Pearson's r test. *P* < 0.05 were considered significant.

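### Assignments are triggered at potential eligibility, from disclosed fixed blocks of 10, with staff unblinded and no concealment described, so selection at entry is possible

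*Combined protocol and SAP*

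**What the plan says.** The Randomization paragraph, under Criteria for Enrollment and Randomization, contains all the relevant statements:

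- Trigger: assignment takes place "Upon potential eligibility being identified".
- Scheme: "subjects will be randomized in 3 blocks of 10 participants and randomized 1:1 to each study arm".
- Delivery: "Randomization will be delivered via a random number generation sequence". This says how the order is produced. It does not say how the order is kept from the people recruiting.
- Blinding: "research staff, clinicians, and patients will not be blinded to patient assignment".
- End of enrolment: "We will enroll until we reach 15 subjects in each study arm who complete all study procedures".

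The Overview of approach gives 30 randomized patients, 15 per arm. Patients come from two centres, and no stratification by centre is mentioned. One exclusion criterion reads "Known history of cognitive impairment or inability to follow study procedures", and its second half is a judgement by staff.

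The documents do not say who generates or holds the list, how the next assignment is released, whether one list serves both centres, or how patients after the third block are assigned.

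**The concern.** Randomization prevents selection bias only if the person deciding on a patient's entry cannot foresee that patient's arm. Here that person may be unblinded, the block length is in the protocol, and the stated trigger comes before eligibility is confirmed. A recruiter who counts assignments within a block can sometimes know the next one and can often guess it better than chance. That knowledge can affect whom to approach, when to approach them, and how to apply a criterion that needs judgement.

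The primary outcome is active minutes read from the pacemaker. An objective reading protects the measurement, but it does not protect the composition of the arms. The intervention is behavioural, so fitness and motivation, which a recruiter can perceive, could plausibly affect active minutes. With 15 patients per arm, a few steered entries could matter.

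**Working it through.** **Inputs.** From the Randomization paragraph: block length 2m = 10 (m = 5), 3 blocks, 1:1. From the Overview of approach: 30 patients, 15 per arm. Assumption: the recruiter sees every earlier assignment in order, at both centres.

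**1. The plan's own figure.** 3 × 10 = 30, or 15 per arm at 1:1. This agrees with the Overview of approach.

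**2. Assignments known with certainty.** Once one arm's m places in a block are used, the rest of the block is known. The expected number per block is 2m/(m + 1) = 10/6 = 1.67. Over three blocks this is 5.0 of 30 (16.7%).

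Enumerating all C(10,5) = 252 orderings gives the number known at the end of a block:

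| Known at end of block | 1 | 2 | 3 | 4 | 5 |
|---|---|---|---|---|---|
| Share of blocks | 55.6% | 27.8% | 11.9% | 4.0% | 0.8% |

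The mean is again 1.67. At least one is always known, so at least 3 of 30. Two or more are known in 44% of blocks.

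**3. Assignments guessed correctly.** The recruiter guesses the arm that is behind and tosses a coin at a tie. Expected correct guesses per block are m + 2^(2m−1)/C(2m,m) − 1/2 = 5 + 512/252 − 0.5 = 6.53. Over three blocks this is 19.6 of 30 (65.3%), against 15 (50%) by chance.

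**4. Other list structures, same formulas, per 30 patients.** The two rows with varying sizes were simulated.

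| Scheme | Certain | Guessed correctly |
|---|---|---|
| Fixed blocks of 4 | 10.0 | 21.3 |
| Fixed blocks of 6 | 7.5 | 20.5 |
| Fixed blocks of 10 (plan) | 5.0 | 19.6 |
| One list of 15 + 15 | 1.9 | 18.0 |
| Undisclosed sizes 4/6 | none | 20.6 |
| Undisclosed sizes 4/6/8 | none | 20.2 |

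Withholding the sizes removes certainty but not better-than-chance guessing. Shorter blocks are worse than 10. One long list is modestly better, by 19.6 − 18.0 = 1.6 correct guesses.

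**5. What guessing could do (illustration only).** Suppose staff shift the mean prognosis of entrants by +η SD when they expect counselling and −η SD when they expect usual care. The expected bias between arms is then 2(2p − 1)η, where p is the share guessed correctly. With p = 0.653 this is 0.61η. For η from 0.1 to 0.5 SD, the bias is 0.06 to 0.31 SD. The documents give no value for η.

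**6. Beyond the third block.** Three blocks supply exactly 30 assignments, but enrolment runs until each arm has 15 completers. Assuming 10% or 20% dropout, 30/0.9 = 33.3 and 30/0.8 = 37.5, so 34 or 38 patients would have to be randomized. The plan does not say how the extra patients are assigned. If the shortfall were filled arm by arm, those assignments would be fully known in advance.

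**The case against.** The other side has a good case on several points.

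- **Most assignments cannot be worked out.** A reader might infer that staff can deduce upcoming assignments in general. They cannot: about 5 of 30 are certain, and the rest are only somewhat better than a coin toss. Even this assumes sight of both centres' assignments, which the documents neither state nor exclude.
- **Ten is a fairly long block.** Shorter blocks would be worse, and longer ones give up balance over time. Block length is a trade-off, not an error.
- **Much of the entry gate is objective.** A device average and a countable step test limit discretion. Patients enrolled at implantation are assessed for randomization on device readings from 3 to 6 months later, so the decision to recruit them comes well before assignment.
- **The baseline is measured.** A reader might infer that no analysis could remove the bias. That is too strong. In a simulation that steered on underlying activity with η = 0.5 and an assumed baseline correlation of 0.7, an unadjusted comparison rejected 10.1% of the time at a nominal 5%. Change from baseline rejected 5.2% and baseline adjustment 5.4%.
- **No error rate can be quoted for this trial.** An unadjusted t-test with 15 per arm simulates at 6.6% for η = 0.25 and 11.0% for η = 0.5. However, η is assumed, and the Data Analyses section plans repeated-measures general linear models over three time points.

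These points limit the size of the concern without removing it. None supplies the missing concealment. Patients with a pacemaker already in place do not have the built-in delay. Baseline activity does not capture motivation, which matters for a counselling intervention.

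**Conclusion.** The point holds as a gap in protection at entry. The stated trigger, together with open and disclosed fixed blocks and no separation of recruiters from the sequence, lets an unblinded recruiter know or guess some assignments before eligibility is settled. The exposure is about 5 of 30 assignments certain and 19.6 of 30 guessed correctly, if staff see all earlier assignments in order. It is lower if they see only their own centre's.

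The resulting bias is possible and of unknown size. Baseline adjustment would deal with the part related to baseline activity only.

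Three further inferences are not supported:

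- That selection bias occurred. The documents show an unprotected route and nothing more.
- That blocks of 10 must be replaced. Their length is defensible, and concealment and timing matter more.
- That every assignment is known once one arm has 15 completers. This follows only if recruitment then continues for the other arm alone, which the plan does not say.

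The change is worth making because it costs almost nothing and closes a route that the analysis could close only in part.

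**What to change.** 1. Change the trigger so that a patient is randomized once consent, all eligibility criteria and the baseline device reading are recorded.
2. Have someone not involved in recruitment generate and hold the list. Keep block details out of documents available to recruiters. The length of 10 is already in the protocol, so for staff who have read it, step 1 carries most of the protection.
3. Release assignments one at a time, by sequentially numbered sealed opaque envelopes or by electronic release. State whether one list serves both centres.
4. Extend the same concealed list beyond 30, so that patients replacing non-completers are also randomized. Do not fill one arm with known assignments.

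Optional: use a longer permuted list in place of blocks of 10. This lowers correct guesses from 19.6 to about 18.0 of 30 for a list of 15 + 15, which would still need extending under step 4. It gives up some balance over time. At patient 15, the SD of the difference in arm sizes would be 2 × √(15 × 0.25 × 15/29) = 2.8. With blocks of 10 it is 2 × √(5 × 0.25 × 5/9) = 1.7.

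Cost: a wording change, a new list and minor administrative work. Final arm sizes may differ slightly from 15:15, because replacements may fall in the arm that is already full.

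### Step counts are to be compared between arms, but the only step counter described is a pedometer issued as part of the counselling treatment

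*Combined protocol and SAP*

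**What the plan says.** The pedometer is introduced in Physical Activity Counseling Intervention Group, item 4 (Assist), part a, as self-monitoring: "A pedometer with a target to increase steps by 10% per week, to a target of 10,000 steps/day". It comes with a recording aid: "A calendar will be given for patients to write down daily amounts".

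The comparator is described under Patient Usual Care. That paragraph abbreviates the group as PAC, although Overview of approach uses PUC for usual care and PAC for the counselling intervention. It reads: "The PAC group will undergo Implanted Medtronic Pacemaker Accelerometer data retrieval, but this data will not be shown to the patient". It adds: "This group will follow their typical clinical routine, and therefore represent a usual care approach". No pedometer, calendar or step visit is mentioned.

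Measurement common to both arms is given under Communication of Physical Activity information: "All individuals with pacemakers will undergo interrogation of their device every 3 months during entire study period". Outcomes names pacemaker active minutes as the primary outcome and does not list steps.

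Data Analyses then states: "Differences in step counts and pedometer determine active time over the study period will be investigated using general linear models for repeated measures". The model is specified "with the randomization group assignment as the between subjects variable" and with "a three factor within subjects comparisons representing the three measurement time points". The same section correlates step counts with PDAH, an abbreviation not expanded in the available text, and does not say which arms contribute.

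**The concern.** A between-arm comparison needs the same quantity measured in the same way in both arms. Here the one described instrument is itself a component of one arm's treatment. It is open to the patient, it carries a rising target, and the trial is unblinded (Randomization).

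The planned step comparison could therefore have no control data. Alternatively, it could get control data only by giving usual-care patients a piece of the intervention. The step-PDAH correlation could also read as a whole-trial result while resting on one arm.

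The consequence is wider than a secondary measure would suggest. The Statistical Methods sentence on the primary outcome is cut short in the available text, so the Data Analyses model is the only outcome model that can be read in full. It names steps and pedometer-based active time, and does not clearly name pacemaker active minutes.

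**Working it through.** The plan gives no figure to reproduce for this point. The check traces every mention of steps or a pedometer to an arm and a time.

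**Step 1. Mentions of steps or a pedometer**

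| Place | What is counted | Arm | When |
|---|---|---|---|
| Criteria for Enrollment and Randomization, inclusion 6 | 650 steps in 10 minutes; counting device not stated | All candidates | Single screening test |
| Counseling Intervention, item 4a | Daily steps on an open pedometer, with a calendar | Counselling only | From the start of the intervention |
| Patient Usual Care | No step measure | – | – |
| Data Analyses | Step counts and pedometer-based active time | Both, by implication of the model | Three time points, not dated |

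The screening test is a walking-ability threshold and cannot supply step counts over the study. The implanted device is described throughout as giving active minutes or active time, never steps.

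**Step 2. Fill the model's cells**

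Two arms at three time points give 2 × 3 = 6 cells. Assume the first time point is baseline (the plan does not say).

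- Usual care: 3 cells, none with a described source.
- Counselling, baseline: 1 cell, no described source. The written prescription carries baseline accelerometer data, not steps. A 10% weekly increase implies a starting count, but its collection before treatment is not described.
- Counselling, later: 6 − 3 − 1 = 2 cells, where the treatment pedometer could supply data.

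At most 2 of the 6 cells have a described source. For pacemaker active minutes, interrogation every 3 months is described for both arms.

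**Step 3. Consequence if only the treatment pedometer exists**

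Write the model as E(Y) = μ + group + time + group × time. With both arms observed, group has 2 − 1 = 1 degree of freedom and group × time has (2 − 1)(3 − 1) = 2. With 0 of 15 usual-care patients supplying steps, only one level of group is observed and both terms drop to 0 degrees of freedom. What remains is a time trend in the counselling arm. The correlation would use at most 15 of the 30 patients.

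**Step 4. Consequence if usual-care patients are given the same pedometer**

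The terms become estimable, but the contrast changes. The usual-care paragraph withholds pacemaker activity data from patients so that it does not alter behaviour. An open pedometer would give them activity feedback by another route. The comparison would become counselling against usual care plus part of the self-monitoring component. The documents give no basis for sizing the resulting dilution.

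**Step 5. The word pedometer in Data Analyses**

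It may be a slip for pacemaker. If so, the active-time part of the model is sound once corrected, and only steps are affected. If it is literal, active time has the same gap as steps, and the one fully readable model omits the primary outcome.

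**The case against.** The strongest reply is that not described is not the same as not collected. Overview of approach refers the reader to Table 1 for procedures and to figures for the schema, and none of these is in the available text. A step-measurement schedule would naturally sit there. The analysis text also points towards step data in both arms: it puts randomized group in the model, has three time points, and sets no arm restriction on the correlation. This stands. A reader might infer that the control arm has no step data, or that the correlation rests on the counselling arm alone; the documents establish neither.

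Second, there is a third possibility besides no control pedometer and the same open pedometer. A separate or masked step counter could have been worn by both arms at the same times. That would be a valid comparison, so it would be wrong to conclude that steps could never be compared. This also stands, although no such device is described.

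Third, the calendar is a self-monitoring aid, and nothing says its entries are the analysed step counts. A reader might infer that the step outcome is self-recorded by unblinded patients; that is plausible but not stated.

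Fourth, steps are not a listed outcome, this is a 30-patient pilot, and the primary outcome data come from the implanted device in both arms. This lowers the severity. It does not answer the mismatch, because a model is still planned on a measure whose only described source belongs to one arm's treatment.

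**Conclusion.** The point holds in limited form. In the available text, the between-arm step analysis has no described source of data for usual care and no described pre-treatment count in either arm. The only described device is part of the counselling treatment. A comparison built on that device is either not estimable (0 of 15 usual-care patients with steps) or not a clean test of counselling against usual care.

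This rests on two conditions: that Table 1 and the figures, which could not be seen, do not describe a separate step measure; and, for the count of at most 2 of 6 cells, that the first time point is baseline.

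The point does not extend to the primary outcome: pacemaker active minutes are collected in both arms and their validity is not in question here. It should be fixed, but it does not undermine the trial's main measurement.

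**What to change.** 1. In Data Analyses, name pacemaker-recorded active minutes as the dependent variable of the between-arm repeated-measures model, and correct or explain the reference to pedometer-based active time.
2. Report treatment-pedometer steps only descriptively, as adherence within the counselling arm.
3. Keep a between-arm step comparison only if a step measure separate from the treatment pedometer was taken in the same way in both arms at the same three time points, including baseline. If so, state the device, whether its display was masked, the wear period and the dates of the time points.
4. State which arms contribute to the step-PDAH correlation, and define PDAH.

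Items 1, 2 and 4 are wording changes and need no new data. The cost is that the between-arm step claim is given up unless the data in item 3 exist. The text should not assert that usual-care patients had no step counter, or label the correlation as counselling-arm only, until the sponsor has confirmed what was collected; if both arms did wear one, those statements would be false and would discard randomized data.

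### The only visible analysis population is an undefined per-protocol set fed by a recruit-until-15-complete rule; active minutes should be analysed in all randomised patients

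*Combined protocol and SAP*

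**What the plan says.** - **Population.** Data Analyses: "Data will be analyzed on a per protocol basis given that the goal of this pilot". The stated reason is unfinished and no definition follows. No all-randomised or sensitivity set appears in the text available.
- **Recruitment rule.** Randomization: "We will enroll until we reach 15 subjects in each study arm who complete all study procedures". Completion is not defined for either arm.
- **Numbers.** Overview of approach: "Thirty participants will be randomized across 2 parallel groups: an intervention group (n=15), or a Patient Usual Care (PUC) group (n=15". Randomization: "subjects will be randomized in 3 blocks of 10 participants and randomized 1:1 to each study arm".
- **Blinding.** Randomization: "Due to the nature of the trial, research staff, clinicians, and patients will not be blinded to patient assignment".
- **Tasks on the intervention arm.** Agree step: "Those patients who agree enter into a shared decision making process to behavior change". Assist step: a pedometer with a step target, and "A calendar will be given for patients to write down daily amounts". Overview: "All subjects in the intervention arm will be contacted every 2 weeks to assess how they are doing with respect to the intervention".
- **Outcome data.** The primary outcome is active minutes from the implanted pacemaker. The Overview and the Communication of Physical Activity information paragraph plan interrogation every 3 months, in everyone with a pacemaker and through both phases, either remotely or in clinic.
- **Analysis.** In Statistical Methods the sentence on comparing the primary outcome breaks off. Data Analyses gives a repeated-measures general linear model for step counts and pedometer active time, and a 0.05 significance threshold.

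**The concern.** Completion happens after randomisation. A comparison restricted to completers keeps the protection of randomisation only if the reasons for not completing are unrelated to outcome, or act alike in both arms. Neither can be taken for granted here. Staff and patients know the allocation. Only the intervention arm has to agree to behaviour change, follow a pedometer target, fill in a calendar and take regular calls. If completing includes those tasks, the intervention completers may be the more motivated part of that arm, set against a usual-care arm that was asked for much less. Part of any difference in active minutes would then reflect who stayed.

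Calling the study a pilot does not remove the problem, because the plan still tests between groups at the 0.05 level.

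**Working it through.** **1. The plan's counts.** 3 blocks × 10 = 30, and 1:1 allocation gives 15 + 15, which reproduces the stated 30. Spare places: 30 − (15 + 15) = 0. The 30 therefore meets the completer rule only if nobody fails to complete.

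The documents give no non-completion rate. If each patient fails to complete with an assumed probability of 5% or 10%, the chance that at least one of 30 does so is 1 − 0.95^30 = 79% or 1 − 0.90^30 = 96%. To reach 15 completers in an arm with loss share a, the expected number randomised but left out is 15a/(1 − a): 1.7, 3.8 and 6.4 at 10%, 20% and 30%.

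**2. Possible bias.** Every input in this step is an assumption, because the documents give no dropout rate, SD or effect size. Assume no true effect and 15 v 15 completers compared by a two-sample t-test, two-sided 5%. Let a be the loss share in the intervention arm (none in usual care), r the correlation of motivation with the analysed outcome, and ρ the correlation of dropout with motivation (ρ = 1 means that every loss comes from the least motivated tail).

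- Bias in SD units = ρ · r · φ(z_a)/(1 − a), with φ(z_a) = 0.175, 0.280 and 0.348 at a = 0.1, 0.2 and 0.3.
- Rejection rate from the noncentral t, 28 df, noncentrality = bias/√(2/15).
- Example: ρ = 1, r = 0.5, a = 0.3 gives 0.5 × 0.348/0.7 = 0.248 SD; noncentrality 0.248/0.365 = 0.68; rejection 10.1%.

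| ρ | r | Bias at a = 0.1 / 0.2 / 0.3 (SD) | Rejection rate |
|---|---|---|---|
| 1 | 0.3 | 0.058 / 0.105 / 0.149 | 5.3% / 5.9% / 6.8% |
| 1 | 0.5 | 0.097 / 0.175 / 0.248 | 5.8% / 7.5% / 10.1% |
| 0.5 | 0.3 | 0.029 / 0.052 / 0.075 | 5.1% / 5.2% / 5.4% |
| 0.5 | 0.5 | 0.049 / 0.087 / 0.124 | 5.2% / 5.6% / 6.3% |

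Simulation allowing for the smaller variance after selection gave 5.2%-10.4% for ρ = 1 and 5.1%-6.3% for ρ = 0.5.

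If usual care loses half as many, equally selectively, the bias is 0.026-0.111 SD with 5.1%-6.0% rejection (ρ = 1), or 0.013-0.056 SD with 5.0%-5.3% (ρ = 0.5). Equal selective loss in both arms, or no link with outcome, gives zero. If the more motivated leave, the sign reverses. A constant difference in level would largely cancel in a group-by-time comparison, so these figures concern selection on change.

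**3. Effect of using all device readings.** If readings are kept for a random share k of those who stop, the remaining bias is m(1 − a)(1 − k)/(1 − a + ak), where m is the completer bias. For ρ = 1 this is 0.028-0.102 SD at k = 0.5 and 0.011-0.037 SD at k = 0.8. It is zero at k = 1, which follows from the formula.

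**4. Scale.** With 15 per arm, a two-sample t-test has 80% power for a difference of about 1.06 SD.

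**The case against.** The strongest reply has four parts.

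**Incomplete text.** The sentence on the primary comparison is cut off and the reason given for per protocol is unfinished. A definition or an all-randomised set could have stood at either place. That stands: the point can be made only about the text available. The per-protocol sentence as it reads is, however, general and not limited to one outcome.

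**Conditional harm, assumed size.** Bias needs completion to differ by arm and to be linked to change in activity, and the documents show neither. Completion may mean only having the scheduled device readings, in which case the risk is small. Usual care may have a step-measurement task too, since step data are compared between groups. The exclusions (follow-up elsewhere, short life expectancy, inability to follow procedures, no stable internet) and remote interrogation should limit losses. The 10.1% figure sits at the extreme of the assumptions, and even the largest bias is well below the 1.06 SD the trial could reliably detect. All of this stands. It limits the severity but does not justify leaving both terms undefined.

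**The visible model is for other outcomes.** The repeated-measures model is stated for step and pedometer data, not for pacemaker minutes. That stands. The advice on the model for active minutes is a precaution, and the fix does not fully cover the step outcomes.

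**Estimand and counts.** Per protocol answers a different question, and 30 can be read as a target with replacement. Both are fair. The first is a reason to keep per protocol as secondary. On the second, the plan still does not say how replacements are allocated, and it is the completer rule together with the per-protocol analysis, not the rule alone, that leaves non-completers out.

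**Conclusion.** The concern holds as a risk in the text available. The only stated population is an undefined per-protocol set, recruitment runs on a post-randomisation event, and the counselling tasks fall on one unblinded arm.

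The size cannot be derived from the documents. Across the assumed scenarios it runs from zero to 0.25 SD, with rejection from 5% to about 10%, and the upper end needs heavy, fully selective loss confined to one arm. The direction is not established either. The mismatch in the counts needs no such assumption: one non-completer requires an allocation beyond the three planned blocks.

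This should be fixed, because the better analysis uses data already planned. Confidence is medium, given the cut-off text and the undefined meaning of completion.

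**What to change.** - Make the primary analysis of pacemaker active minutes all randomised patients as assigned, using every available device reading, including those after counselling is declined or stopped.
- Use a model that keeps patients with a missing time point, such as a likelihood-based mixed model. A standard repeated-measures general linear model uses only patients with every time point and would return to complete cases.
- Define per protocol and completion separately for each arm, and keep per protocol as a secondary analysis.
- Reconcile the 30 planned randomisations and three blocks with the 15-completer rule, and state how any further patients are allocated.
- Report completion by arm, and agreement to counselling in the intervention arm.

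**Cost.** Protocol and SAP wording, plus carrying on the planned 3-monthly interrogations after counselling stops. Some readings will still be missing through death, withdrawal of consent or device change, and step outcomes remain partly exposed. The all-randomised analysis estimates the effect of being assigned counselling, not of completing it. Data Analyses mixes future and past tense; if data collection had already ended, only readings already collected can be used.
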